10.15 Appendix 15: Tumor Flare Reaction Management Guidance and Grading

Subjects in this study should be monitored for tumor flare reaction (TFR). TFR is defined as a sudden and tender increase in the size of the disease-bearing sites, including the lymph nodes, spleen, and/or the liver often accompanied by low-grade fever, diffuse rash, and in some cases increase in the peripheral blood lymphocyte counts. TFR will be assessed according to the following CTCAE v5 criteria:

- Grade 1: Mild pain
- Grade 2: Moderate pain; limiting instrumental activity of daily life (ADL)
- Grade 3: Severe pain; limiting self-care ADL
- Grade 4: Life-threatening consequences; urgent intervention indicated
- Grade 5: Death

TFR Management Guidelines

Treatment of TFR is up to the discretion of the investigator depending upon the severity and clinical situation. It is suggested that TFR be treated with corticosteroids at the investigator's discretion. NSAIDs (ie, ibuprofen 400 to 600 mg orally every 4 to 6 hours as needed) and/or narcotic analgesics for pain management may also be administered as needed. In mild to moderate cases, it is suggested that GEN3017 is continued along with symptomatic treatment as indicated above. Table 6-4 includes dose modification guidance as it relates to TFR.

Confidential Page 142 of 162

Version: 3.0

Document Number: TMF-380962

Lysis Syndrome

10.16 Appendix 16: Classification and Management of Laboratory and Clinical Tumor

Genmab

Subjects who are considered to have an increased risk for tumor lysis syndrome (TLS), eg, due to the type of lymphoma, the tumor burden (bulky disease and/or elevated LDH), renal impairment and/or elevated uric acid should be considered for hydration and prophylactic treatment with a uric acid lowering agent as well as frequent monitoring, according to local standards or available guidelines (Coiffier et al., 2008).

In addition, close monitoring of laboratory parameters to allow for early diagnosis of possible TLS is recommended at the investigator's discretion. For details, refer to Table 1-1 and Table 1-2 for the minimum sampling time points for tumor lysis. If signs of TLS occur, supportive therapy, including rasburicase, may be used as clinically indicated at the investigator's discretion.

In laboratory TLS, 2 or more metabolic abnormalities (ie, hyperuricemia, hyperkalemia, hyperphosphatemia, and hypocalcemia) must be present during the same 24-hour period within 3 days before the start of therapy or up to 7 days afterward.

Clinical tumor lysis syndrome (CTLS) requires the presence of laboratory TLS **plus** an increased creatinine level, seizures, cardiac dysrhythmia, or death.

Definitions of Laboratory and Clinical Tumor Lysis Syndrome

Metabolic Abnormality	Criteria for Classification of Laboratory TLS	Criteria for Classification of CTLS
Hyperuricemia	Uric acid >8.0 mg/dL (475.8 μmol/liter) in adults or above the upper limit of the normal range for age in children	Not Applicable
Hyperphosphatemia	Phosphorus >4.5 mg/dL (1.5 mmol/liter) in adults or >6.5 mg/dL (2.1 mmol/liter) in children	Not Applicable
Hyperkalemia	Potassium >6.0 mmol/liter or 6 mg/L	Cardiac dysrhythmia or sudden death probably or definitely caused by hyperkalemia
Hypocalcemia	Corrected calcium <7.0 mg/dL (1.75 mmol/liter) or ionized calcium <4.5 mg/dL (1.12 mmol/liter) ^a	Cardiac dysrhythmia, sudden death, seizure, neuromuscular irritability (tetany, paresthesias, muscle twitching, carpopedal spasm, Trousseau's sign, Chvostek's sign, laryngospasm, or bronchospasm), hypotension, or heart failure probably or definitely caused by hypocalcemia
Acute kidney injury ^b	Not applicable	Increase in the serum creatinine level of 0.3 mg/dL (26.5 µmol/liter) (or a single value >1.5 times the upper limit of the ageappropriate normal range if no baseline creatinine measurement is available) or the presence of oliguria, defined as an average urine output of <0.5 ml/kg/hr for 6 hr

CTLS= clinical tumor lysis syndrome; TLS=tumor lysis syndrome.

Note: In laboratory tumor lysis syndrome, 2 or more metabolic abnormalities must be present during the same 24-hour period within 3 days before the start of therapy or up to 7 days afterward. Clinical tumor lysis syndrome requires the presence of laboratory tumor lysis syndrome plus an increased creatinine level, seizures, cardiac dysrhythmia, or death.

Confidential Page 143 of 162

Document Number: TMF-380962

Version: 3.0

a. The corrected calcium level in milligrams per deciliter = measured calcium level in milligrams per deciliter $+0.8\times(4-\text{albumin in grams per deciliter})$.

b. Acute kidney injury is defined as an increase in the creatinine level of at least 0.3 mg per deciliter (26.5 μmol per liter) or a period of oliguria lasting 6 hours or more. By definition, if acute kidney injury is present, the subject has clinical tumor lysis syndrome. Data about acute kidney injury are from (Levin et al., 2007)

Source: (Howard et al., 2011)

Cairo-Bishop Definition of Clinical Tumor Lysis Syndrome and Grading

Complication	Grade 1	Grade 2	Grade 3	Grade 4	Grade 5
Creatinine ^a	1.5×ULN	> 1.5–3.0×ULN	> 3.0-6.0×ULN	> 6.0×ULN	
Cardiac arrhythmia	Intervention not indicated	Nonurgent medical intervention needed	Symptomatic and incompletely controlled medically or controlled with device (eg, defibrillator)	Life-threatening (eg, arrhythmia associated with CHF, hypotension, syncope, shock)	
Seizure	None	One brief generalized seizure; seizure(s) well controlled by anticonvulsants or infrequent focal motor seizures not interfering with ADL	Seizure in which consciousness is altered; poorly controlled seizure disorder; with breakthrough generalized seizures despite medical intervention	Seizure of any kind which are prolonged, repetitive or difficult to control (eg, status epilepticus, intractable epilepsy)	Death

ADL=activities of daily living; CHF=congestive heart failure; ULN=upper limit of normal.

Source: (Coiffier et al., 2008)

Confidential Page 144 of 162

a. If no institutional ULN is specified, ULN is defined as follows: female 105.6 μ mol/L, male 114.4 μ mol/L.

Version: 3.0

Recommendations for Initial Management of Electrolyte Imbalances and Prevention of Tumor Lysis Syndrome

Genmab

Tumor Lysis Syndr	
Abnormality	Management Recommendations
· · · · · · · · · · · · · · · · · · ·	ing rapidly rising potassium)
Potassium ≥0.5 mmol/L increase from prior value (even	Re-check potassium, phosphorus, uric acid, calcium and creatinine in 1 hour STAT. If further ≥0.2 mmol/L increase in potassium, but still < upper limit of normal (ULN), manage as per potassium ≥ ULN. Otherwise re-check in 1 hour.
if potassium within normal limits [WNL])	Resume per protocol testing if change in potassium is <0.2 mmol/L, and potassium < ULN, and no other evidence of tumor lysis syndrome.
	At the discretion of the investigator, consider re-checking tumor lysis syndrome (TLS) laboratory values prior to hospitalization. If stable or decreased, and still within normal limits (WNL), hospitalization is at the discretion of the investigator. Potassium, phosphorus, uric acid, calcium and creatinine must be re-checked within 24 hours.
Potassium > upper	Perform STAT electrocardiogram (ECG) and commence telemetry.
limit of normal	Nephrology (or other acute dialysis service) notification with consideration of initiating dialysis.
	Administer Kayexalate 60 g (or Resonium A 60 g).
	Administer furosemide 20 mg intravenously (IV) × 1.
	Administer calcium gluconate 100 – 200 mg/kg IV slowly if there is ECG/telemetry evidence of life-threatening arrhythmias.
	Re-check potassium, phosphorus, uric acid, calcium and creatinine in 1 hour STAT.
	If potassium < ULN 1 hour later, repeat potassium, phosphorus, uric acid, calcium and creatinine 1, 2 and 4 hours, if no other evidence of tumor lysis syndrome.
Potassium	Perform STAT ECG and commence telemetry.
≥6.0 mmol/L (6.0 mEq/L) and/or symptomatic	Nephrology (or other acute dialysis service) assessment with consideration of initiating dialysis.
(eg, muscle cramps,	Administer Kayexalate 60 g (or Resonium A 60 g).
weakness,	Administer furosemide 20 mg IV × 1.
paresthesias, nausea,	Administer insulin 0.1 U/kg IV + D25 2 mL/kg IV.
vomiting, diarrhea)	Administer sodium bicarbonate $1 - 2$ mEq/kg IV push.
	If sodium bicarbonate is used, rasburicase should not be used as this may exacerbate calcium phosphate precipitation.
	Administer calcium gluconate 100 – 200 mg/kg IV slowly if there is ECG/telemetry evidence of life-threatening arrhythmias. Do not administer in same IV line as sodium bicarbonate.
	Re-check potassium, phosphorus, uric acid, calcium and creatinine every hour STAT.
Hyperuricemia	
Uric acid ≥8.0 mg/dL	Consider rasburicase (dose per institutional guidelines).
(476 μmol/L)	If rasburicase is used, sodium bicarbonate should not be used as this may exacerbate calcium phosphate precipitation.
	Re-check potassium, phosphorus, uric acid, calcium and creatinine in 1 hour STAT.
Uric acid ≥10 mg/dL (595 µmol/L) OR Uric acid ≥8.0 mg/dL (476 µmol/L) with 25% increase and	Administer rasburicase (dose per institutional guidelines).
	If rasburicase is used, sodium bicarbonate should not be used as this may exacerbate calcium phosphate precipitation.
	Notify nephrology (or other acute dialysis service).
creatinine increase	Re-check potassium, phosphorus, uric acid, calcium and creatinine in 1 hour STAT.
≥0.3 mg/dL (≥0.027 mmol/L) from predose level	If uric acid <8.0 mg/dL 1 hour later, repeat potassium, phosphorus, uric acid, calcium and creatinine 2 and 4 hours later, if no other evidence of tumor lysis.

Confidential Page 145 of 162

Document Number: TMF-380962

Version: 3.0

Abnormality	Management Recommendations
Hypocalcemia	
Calcium ≤7.0 mg/dL (1.75 mmol/L) AND Patient symptomatic (eg, muscle cramps, hypotension, tetany, cardiac arrhythmias)	Administer calcium gluconate 50 – 100 mg/kg IV slowly with ECG monitoring. Telemetry. Re-check potassium, phosphorus, uric acid, calcium and creatinine in 1 hour STAT. If calcium normalized 1 hour later, repeat potassium, phosphorus, uric acid, calcium and creatinine 2 and 4 hours later, if no other evidence of tumor lysis. Calculate corrected calcium and check ionized calcium if albumin is low.
Hyperphosphatemia	
Phosphorus ≥5.0 mg/dL (1.615 mmol/L) with ≥0.5 mg/dL (0.16 mmol/L) increase	Administer a phosphate binder (eg, aluminum hydroxide, calcium carbonate, sevelamer hydroxide, or lanthanum carbonate). Nephrology (or other acute dialysis service) notification (dialysis required for phosphorus ≥10 mg/dL). Re-check potassium, phosphorus, uric acid, calcium and creatinine in 1 hour STAT. If phosphorus <5.0 mg/dL 1 hour later, repeat potassium, phosphorus, uric acid, calcium and creatinine 2 and 4 hours later, if no other evidence of tumor lysis syndrome.
Creatinine	
Increase ≥25% from baseline	Start or increase rate of IV fluids. Re-check potassium, phosphorus, uric acid, calcium and creatinine in 1 – 2 hours STAT.

ECG=electrocardiogram; IV=intravenous; TLS=tumor lysis syndrome.

Confidential Page 146 of 162

Version: 3.0

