		refractory ^a grade 3 for >72 hours or grade 4	Manage CRS per current practice guidelines (Section 10.13) and provide supportive therapy, which may include intensive care.
	ICANS (see Section 10.14)	Grade 1 and grade 2	Withhold GEN3017 until resolution of ICANS event to ≤ grade 1 for at least 72 hours.
			Provide supportive therapy and manage per current practice guidelines.
		Grade 3	Withhold GEN3017 until resolution of ICANS event to ≤ grade 1 for at least 72 hours.
			Provide supportive therapy, which may include intensive care, consider neurology evaluation, and manage per current practice guidelines.
			Recurrent grade 3 ICANS: Permanently discontinue GEN3017.
		Grade 4	Permanently discontinue GEN3017.
			Provide supportive therapy, which may include intensive care, consider neurology evaluation, and manage per current practice guidelines.
Hematological (see Section 6.7.2.1 for details) ^b	Platelet count decreased/	≥ Grade 3	Withhold GEN3017 until platelet count is ≥50 × 10 ⁹ /L.
	thrombocytopenia		Platelet infusions may be administered per institutional standards.
	Neutropenia and febrile neutropenia	≥ Grade 3	Withhold GEN3017 until neutrophil count is $\geq 0.5 \times 10^9 / L$.
			Use of growth factors is mandated.
	Anemia	≥ Grade 3	Withhold GEN3017 until hemoglobin is ≥8 g/dL (≥80 g/L or ≥4.9 mmol/L).
			Red blood cell infusions should be administered per institutional standards.

Confidential Page 78 of 162

Document Number: TMF-380962

Version: 3.0

	Adverse Event(s)	Toxicity Grade or Condition (CTCAE v5.0 Except ASTCT for CRS/ICANS and Cairo- Bishop for TLS/CTLS)	Adverse Event Management	
	TLS/CTLS	Any grade	Withhold GEN3017 until resolution of TLS/CTLS event.	
	Tumor flare reaction	Grade 3 and 4	Withhold GEN3017 until improvement to ≤ grade 1. Monitor for signs and symptoms of compression or obstruction due to mass effect secondary to tumor flare, and institute appropriate treatment (Section 10.15).	
	All other non- hematologic AEs	Grade 3a; first occurrence	Withhold GEN3017 until improvement to ≤ grade 2 or resolution to baseline.	
		Grade 3a; recurrent	Second episode of the same AE considered related to GEN3017:	
Other non-hematologic			Withhold GEN3017 until improvement to ≤ grade 2 or resolution to baseline.	
			Permanently discontinue GEN3017 if no improvement within 14 days unless otherwise agreed upon with the sponsor's medical monitor.	
		Grade 4a; first occurrence	Withhold GEN3017.	
			Initiate proper management of the AE.	

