8.4.1.1 Adverse Events of Special Interest

The protocol-defined AESIs are:

- 1. CRS, graded according to ASTCT criteria ((Lee et al., 2019); Section 10.12 and Section 10.13)
- 2. ICANS, graded as ASTCT Criteria ((Lee et al., 2019); Section 10.14)
- 3. CTLS graded according to Cairo-Bishop ((Coiffier et al., 2008); Section 10.15)

Additional AESIs may be defined on the basis of an ongoing review of the safety data.

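### Appendix 16 gives two incompatible case definitions for clinical tumor lysis syndrome, a wrong second potassium unit, and is missed by the cross-references meant to reach it

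*Combined protocol and SAP*

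**What the plan says.** All of the conflicting text is in Section 10.16 (Appendix 16).

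- **Body text and table note.** Laboratory TLS is two or more of four metabolic abnormalities, which "must be present during the same 24-hour period within 3 days before the start of therapy or up to 7 days afterward". The note under the definitions table then states: "Clinical tumor lysis syndrome requires the presence of laboratory tumor lysis syndrome plus an increased creatinine level, seizures, cardiac dysrhythmia, or death". The body text says the same.
- **Footnote b**, attached to the acute kidney injury row: "Acute kidney injury is defined as an increase in the creatinine level of at least 0.3 mg per deciliter", or oliguria of 6 hours or more. It continues: "By definition, if acute kidney injury is present, the subject has clinical tumor lysis syndrome".
- **Hyperkalemia criterion** in the definitions table: "Potassium >6.0 mmol/liter or 6 mg/L". The management table later in the same appendix has: "≥6.0 mmol/L (6.0 mEq/L) and/or symptomatic".
- **Cairo-Bishop grading table.** The lowest creatinine grade is at 1.5×ULN. Default ULNs are 105.6 µmol/L (female) and 114.4 µmol/L (male).

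Other sections rely on this appendix. Section 8.4.1.1 lists the third AESI as "CTLS graded according to Cairo-Bishop". Section 8.4.3.5 requires AESIs to be reported within 24 hours if serious and 72 hours if not. The TLS/CTLS row of Table 6-4, for any grade, reads: "Withhold GEN3017 until resolution of TLS/CTLS event". Sections 2.3.2, 6.6.3.1, 6.7.1 and 8.4.1.1 all point TLS readers to Section 10.15, which is the tumor flare appendix.

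**The concern.** A named AESI should have one case definition. Here two sentences a few lines apart give different answers for a subject whose creatinine rises without laboratory TLS. Such rises are foreseeable in this trial: the protocol anticipates cytokine release syndrome with hypotension, contrast-enhanced CT and NSAIDs for tumor flare.

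One site could record the event as CTLS, report it as an AESI and hold drug under the any-grade row. Another could record a creatinine increase as an ordinary adverse event, where the general non-hematologic row of Table 6-4 starts at grade 3. The CTLS count and the holds that follow from it would then depend partly on which sentence was read. The misdirected cross-references make this more likely, because a reader who follows them does not reach the TLS definitions at all.

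**Working it through.** **1. The two CTLS rules side by side**

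| Subject | Body text and table note | Footnote b |
|---|---|---|
| Laboratory TLS and creatinine rise ≥0.3 mg/dL | CTLS | CTLS |
| Laboratory TLS, no clinical criterion | not CTLS | not CTLS |
| Creatinine rise ≥0.3 mg/dL, all four metabolic values normal | not CTLS | CTLS |
| Creatinine rise ≥0.3 mg/dL well after day 7 of therapy | not CTLS (laboratory TLS window closed) | CTLS |

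The rules disagree only for acute kidney injury without laboratory TLS. In that group footnote b can only add cases. The number added is N × p, where p is the proportion of subjects with such an injury. The documents give no value for p, so the number cannot be computed.

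**2. The potassium units**

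Input not in the documents: molar mass of potassium, 39.098 g/mol (physical constant).

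- 6 mg/L ÷ 39.098 = 0.153 mmol/L.
- 6.0 mmol/L × 39.098 = 234.6 mg/L, so the two printed values differ by a factor of about 39.
- 3.5 mmol/L × 39.098 = 136.8 mg/L, far above 6 mg/L.

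As a control, the other unit pairs in the same table convert to the printed values, allowing for rounding: uric acid 8.0 mg/dL = 475.9 µmol/L (printed 475.8); phosphorus 4.5 and 6.5 mg/dL = 1.45 and 2.10 mmol/L (printed 1.5 and 2.1); calcium 7.0 mg/dL = 1.75 mmol/L; ionized calcium 4.5 mg/dL = 1.12 mmol/L; creatinine 0.3 mg/dL = 26.5 µmol/L. Only the potassium pair fails. The management table's pair, 6.0 mmol/L and 6.0 mEq/L, is consistent.

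If the mg/L limb were applied literally, hyperkalemia would always be met and laboratory TLS would fall from two of four abnormalities to one of the other three. CTLS under the note would still need a clinical criterion.

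**3. The definition against the grading table**

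- Grade 1 creatinine: 1.5 × 105.6 = 158.4 µmol/L (female); 1.5 × 114.4 = 171.6 µmol/L (male).
- A 0.3 mg/dL rise from an assumed baseline of 70 µmol/L gives 70 + 26.5 = 96.5 µmol/L, below both default ULNs.
- For that rise alone to reach grade 1, baseline would have to be at least 158.4 − 26.5 = 131.9 µmol/L (female) or 171.6 − 26.5 = 145.1 µmol/L (male), both already above the ULN.

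A subject can therefore meet the creatinine criterion and have no creatinine grade on the scale that Section 8.4.1.1 requires. This gap exists under either CTLS rule, because the acute kidney injury row itself uses the 0.3 mg/dL rise.

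**4. Reach into DLTs**

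Section 6.7.1 counts TLS as a DLT only at grade 4, or at grade 3 unresolved within 5 days. By creatinine, grade 3 starts above 3.0×ULN: 3.0 × 105.6 = 316.8 µmol/L (female) or 3.0 × 114.4 = 343.2 µmol/L (male). The rises on which the two sentences disagree most easily are far below that.

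**The case against.** The best defence is that footnote b should be read in place. It annotates the acute kidney injury row of the CTLS column, directly beneath a note that requires laboratory TLS, so it may mean only that kidney injury satisfies the clinical limb. That reading is reasonable, and many sites may adopt it. But the footnote does not say so, and its wording that the classification follows by definition invites the opposite reading. The table's attribution to a published source does not settle which sentence governs in this trial.

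It is also fair that adverse events are recorded as investigator diagnoses (Section 10.2), and that nothing in Section 9.3.4 derives CTLS by program from this table. This limits the likely effect. It does not remove it, because the investigator is sent to the protocol for the definition. One could add that an event with no Cairo-Bishop grade is simply not a Cairo-Bishop event. The grading table cannot serve as the tie-breaker, though, since it also leaves a 0.3 mg/dL rise ungraded in a subject who does have laboratory TLS.

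Three stronger readings are tempting and are not supported:

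- **The potassium slip makes everyone a case.** The first value, 6.0 mmol/L, is consistent with the management table, and sites working in mmol/L or mEq/L are unaffected. The slip alone cannot create laboratory TLS or CTLS. The printed unit should also be checked against the PDF, since the text reviewed was machine-read.
- **The DLT endpoint is compromised.** Only high-grade TLS counts. Other non-hematologic toxicity of grade 3 or higher is already a DLT subject to listed exclusions, so the label rarely changes DLT status.
- **Most recorded CTLS would be false.** That needs rates of true CTLS and of other kidney injury, which the documents do not give.

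**Conclusion.** The contradiction is real and sits in operative text. Footnote b and the body text with its note cannot both be applied to a subject with acute kidney injury and no laboratory TLS, and no other section says which prevails. What is affected is the consistency of the CTLS AESI count and of the any-grade hold in Table 6-4. The direction, if footnote b is applied literally, is toward more CTLS; the size cannot be derived from the documents. The effect on DLTs is small, and no sample size or primary efficacy analysis changes. The potassium unit and the cross-references are secondary errors of the same kind. The unit conclusion rests on one physical constant; the rest is a reading of the text.

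**What to change.** Four wording changes:

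1. Reconcile footnote b with the body text and table note, so that one stated CTLS definition governs AESI reporting and the AESI tables. Because the definition also feeds the Table 6-4 hold, the choice is the sponsor's. The point is that the passages must agree.
2. Correct the second potassium unit in the definitions table so that it agrees with the first value and with the management table (6.0 mmol/L, 6.0 mEq/L).
3. Redirect the TLS cross-references in Sections 2.3.2, 6.6.3.1, 6.7.1 and 8.4.1.1 from Section 10.15 to Section 10.16. References to 10.15 for tumor flare stay as they are.
4. Reconcile the CTLS definition with the Cairo-Bishop table, so that it is clear how an event below its 1.5×ULN starting point relates to the required grading and to the any-grade row of Table 6-4.

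The cost is a document update, carried through to the eCRF completion guideline and the statistical analysis plan. No new data are needed, and clinically significant creatinine rises remain reportable as adverse events in any case.

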10.17 Appendix 17: Statistical Methodologies

An mBOIN design will be utilized to guide optimal recommendation for dose escalation at the end of each dose level. Compared to a classical 3+3 design, the mBOIN design allows reescalation to an already investigated dose level and it also ensures that a dose level is terminated due to toxicity as a dose level can no longer be investigated if an additional DLT-free DL would lead to de-escalation. Thus, with the mBOIN design the number of subjects on a toxic dose level is limited.

Genmab

For cohorts with 3 DLT-evaluable subjects, the decision during escalation will be consistent with the '3+3' design (ie, escalate if no DLT, remain on same dose level if 1 DLT, de-escalate if 2 DLTs and terminate dose level if 3 DLTs).

Operational characteristics in terms of subjects treated for the mBOIN design are given below. These are based on 4 different toxicity scenarios, when assuming 10 dose levels, and 100000 simulations.

		DL1	DL2	DL3	DL4	DL5	DL6	DL7	DL8	DL9	DL10	Total subjects
1	Prob (DLT)	0	1%	1%	2%	3%	4%	5%	10%	20%	30%	
	Subjects treated	1	1.1	1.1	3.2	3.3	3.4	3.8	5.2	6.1	4.7	32.9
2	Prob (DLT)	1%	2%	4%	8%	16%	24%	32%	35%	40%	45%	
	Subjects treated	1.1	1.2	1.6	4.8	5.8	5.2	3.1	1.4	0.5	0.2	24.8
3	Prob (DLT)	1%	2%	10%	15%	20%	25%	30%	35%	40%	45%	
	Subjects treated	1.1	1.4	2.9	5.5	5.0	3.8	2.3	1.1	0.4	0.1	23.5
4	Prob (DLT)	1%	2%	10%	15%	20%	25%	30%	40%	50%	60%	
	Subjects treated	1.1	1.4	2.9	5.5	5.0	3.8	2.4	1.1	0.3	0	23.4

DL=dose level; DLT=dose-limiting toxicity.

Confidential Page 147 of 162

Genmab

Document Number: TMF-380962

Version: 3.0

